#### **Secondary end-points:**

Change in NRD from peak exacerbation (hospital) to recovery baseline (home)

Correlation of time to recovery as measured by NRD and EXACT-PRO

Correlation of NRD, EXACT-PRO and daytime activity from hospital discharge to recovery

Physician-assessed exacerbation within 30-day post-discharge

Self-treated exacerbation within 30-day post-discharge

All cause hospital readmission within 30-day post-discharge

Mortality within 30-day post-discharge

Recovery as defined by the EXACT-PRO within 30-day post-discharge

Medication change within 30-day post-discharge

Unplanned healthcare contacts

Attendance of emergency department (without admission)

**Trial design**

This study will be an observational cohort design.

## 7.2 Flowchart

	Screen Visit	Day 1	Hospital measurements	Pre-discharge	Home measurements
Patient information and informed consent	X				
Medical history		X		X	
Comorbidities					
Smoking history					
Premorbid data					
Medications		X		X	
Blood tests		X		X	
Chest x-ray		X			
Demographics: Age, height, weight, FFM		X			
Vital observations		X	X	X	
Questionnaires: EXACT-PRO CAT (weekly)		X	X	X	X
Spirometry: FEV 1 , FVC, IC		X		X	X (weekly)
Neural respiratory drive		X	X	X	X
Physical activity watch issued				X	

## 8 Subject selection

**Target population**

Patients admitted to hospital with a primary diagnosis of an acute exacerbation of COPD.

**Screening and eligibility assessment**

Patients will be identified by the clinical team and enrolled in the study within 16 hours of hospital admission to St Thomas' Hospital as study participants. All efforts will be made to reduce disruption of care and respect patient privacy. Interruption of patient care will be minimized by making sure that study staff only approach potential participants after their initial triage and decision to admit. Study related procedures will commence only after the informed consent form is signed by the subject. The study will be explained to the potential participant and sufficient time provided to the subject to ask questions regarding the study (minimum 1 hour). Before signing the consent form, the participant will also be shown the Patient Information Sheet that details the steps of the study procedure to them.

If the participants develop any of the exclusion criteria listed below between enrolment and as the study proceeds, they will be asked to discontinue from the study.

Approximately 300 patients are admitted with COPD per year. Based on previous research conducted by the group in this area there would be expected to be 4-5 eligible patients per week with 2 patients recruited each week.

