## 8.2 Subject exclusion criteria

### Exclusion criteria

- Previous home PAP (CPAP or NIV) therapy use within the past year, or post-discharge
- Allergies to latex, metals or local anaesthetic agents
- Wound or inflamed skin at parasternal location (2nd intercostal space)
- History of skin allergies or sensitivity to cosmetics and lotions
- Psychological and social factors that would impair compliance with study protocol and schedule
- Any major non-COPD chronic disease or condition, such as severe heart failure (LVEF<30%), malignancy (active treatment or palliation), end stage renal failure/dialysis, significant neuromuscular disease (e.g. Motor Neuron Disease, Muscular Dystrophy) determined by review of medical history and / or patient reported medical history that may contribute significantly to risk of readmission, as determined by PI
- Length of stay  $\leq 24$  hours
- Planned travel away from home within the 30 day post discharge period

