#### **9.6 End of Study Definition**

The trial will cease when the final patient has completed 30 days of home monitoring or has an exacerbation requiring hospital re-admission or 12 months from trial initiation, whichever is sooner.

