### **12.2 Withdrawal / dropout of subjects**

Each participant has the right to withdraw from the study at any time. In addition, the investigator may discontinue a participant from the study at any time if the investigator considers it necessary for any reason including:

- Ineligibility (either arising during the study or retrospective having been overlooked at screening)

- Disease progression which requires discontinuation of the study medication or results in inability to continue to comply with study procedures
- Consent withdrawn
- Lost to follow up

The reason for withdrawal will be recorded in the CRF.

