## **14 Statistical considerations**

### **14.1 Sample size calculation (some pilot/feasibility studies may not require a formal sample size calculation)**

A sample size of 30 has been set. This study is a pilot feasibility study with no prior data to power the sample size. As such, the sample size was not determined based on power analysis but will provide sufficient data to inform a larger future study. Data collected during this study will be used for sample size calculation for validation of future work. Recruitment will continue until 30 patients have completed the study.

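### Section 8 asks participants who meet an exclusion criterion after enrolment to leave the study, and the protocol does not provide for collecting their 30-day outcomes

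*Protocol*

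**What the plan says.** Under Screening and eligibility assessment, Section 8 states that participants who "develop any of the exclusion criteria listed below between enrolment and as the study proceeds, they will be asked to discontinue from the study". The sentence covers every listed criterion and refers to the study as a whole.

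Section 12.2 is permissive: "the investigator may discontinue a participant from the study at any time if the investigator considers it necessary". Its list of reasons includes ineligibility that arises during the study. About what follows, it says: "The reason for withdrawal will be recorded in the CRF".

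Section 14.1 sets the recruitment target: "Recruitment will continue until 30 patients have completed the study". It does not say when a participant counts as having completed. The nearest text is the end-of-trial definition in 9.6, under which the trial ends when "the final patient has completed 30 days of home monitoring or has an exacerbation requiring hospital re-admission", or at 12 months if sooner.

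Section 9.4 contains two outcome checks. The medical record review is there to corroborate events that patients report, and health status is confirmed at the day-30 visit. Section 7.1 lists physician-assessed and self-treated exacerbation, all-cause readmission and mortality, each within 30 days of discharge, as secondary endpoints.

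**The concern.** Some exclusion criteria carry information when they arise after enrolment. Three in 8.2 can plausibly do so during home follow-up:

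- **Inflamed skin at the electrode site.** Section 11 warns that the pads and cleaning cream may irritate, so the study procedure itself could bring a participant within this criterion.
- **Home positive airway pressure.** The criterion expressly extends to the period after discharge. Starting such therapy is part of the clinical course.
- **Compliance.** The criterion reads "Psychological and social factors that would impair compliance with study protocol and schedule". In a pilot that asks how workable NRD measurement is at home, this is a feasibility result.

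If such participants leave the study and nobody looks up what happened to them, their 30-day exacerbation, readmission and mortality are missing. An analysis plan can choose the denominator later. It cannot recover outcomes that were not collected. Section 14.1 intends these data to feed the sample size of a later study, so gaps in event rates would carry forward.

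**Working it through.** **Plan's own figure.** The 30 cannot be re-derived. Section 14.1 says it was not based on a power analysis and gives no effect size or variance. The check is therefore a reading of the text, followed by illustrative arithmetic.

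**Reading the passages together.**

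1. Section 8 asks for discontinuation from the study. Section 12.2 allows it and requires the reason to be recorded.
2. The adverse event definition in Section 11 covers the time when participants are taking part, so it does not supply outcomes after they leave.
3. The record review in 9.4 starts from patient-reported events, and the health-status check takes place at a day-30 visit. Neither is written to reach someone who has left.
4. Recruitment under 14.1 continues to 30 completers, so those who stop are in effect replaced in the recruitment count.

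**Inputs.** 30 completers (14.1). Readmission of 20% (Section 11, which says within 28 without a unit, taken here as days). Discontinuation is not stated, so 5%, 10% and 20% are assumed.

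**Starters needed** = 30/(1 − d). This gives 30/0.95 = 31.6, 30/0.90 = 33.3 and 30/0.80 = 37.5, rounded up to 32, 34 and 38. The number of stoppers, k, is then 2, 4 or 8.

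**Bounds on readmission among all starters**, if 6 of 30 completers are readmitted (20%) and the stoppers' outcomes are unknown: lower 6/(30 + k), upper (6 + k)/(30 + k).

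| k | Completing, 30/(30 + k) | Lower | Upper |
|---|---|---|---|
| 2 | 93.8% | 6/32 = 18.8% | 8/32 = 25.0% |
| 4 | 88.2% | 6/34 = 17.6% | 10/34 = 29.4% |
| 8 | 78.9% | 6/38 = 15.8% | 14/38 = 36.8% |

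**Unequal loss.** Let the true rate among starters be p = 0.20, with loss a in those readmitted and b in the others. The rate among completers is p(1 − a)/[p(1 − a) + (1 − p)(1 − b)].

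- a = b = 0.10: 0.18/(0.18 + 0.72) = 20.0%, no bias.
- a = 0.10, b = 0.05: 0.18/(0.18 + 0.76) = 19.1%.
- a = 0.20, b = 0.05: 0.16/(0.16 + 0.76) = 17.4%.
- a = 0.30, b = 0.05: 0.14/(0.14 + 0.76) = 15.6%.

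The exact (Clopper-Pearson) 95% interval for 6 of 30 is 7.7–38.6%, and every figure above lies inside it. The two illustrations use the 20% differently: as the completers' rate in the bounds, and as the starters' rate in the unequal-loss cases. They should not be compared with each other.

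**Meaning of completed.** If readmitted patients did not count as completers, about 30/0.80 = 37.5, or 38 patients, would be needed on that ground alone. If they count, as 9.6 suggests, this inflation does not arise.

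**The case against.** Much of the case on the other side stands.

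- **Completer-only analysis.** A reader might infer from 14.1 that only the 30 completers will be analysed. The text does not support this. It is a recruitment stop, the endpoints in 7.1 are not limited to completers, and under 10.5 the CRF covers everyone recruited.
- **Discarded data or forbidden follow-up.** Neither is stated. Withdrawal reasons and adverse events during participation are recorded, and nothing says that earlier NRD data are dropped. The participant information sheet and consent form, not seen here, may also deal with record access after withdrawal. The claim is limited to the protocol as shown.
- **Completion wholly undefined.** Section 9.6 gives a usable reading, 30 days or readmission, although it is worded for the final patient. Deaths and discontinuations remain open.
- **The major-disease criterion.** Because it mentions readmission risk, it is tempting to cite it as outcome-related selection. It concerns major non-COPD disease found from the medical history, which is largely a screening judgement and would seldom arise anew within 30 days.
- **Unavoidable exclusions.** Enrolment is within 16 hours of admission, so a stay of 24 hours or less can only be known afterwards. That is a deferred eligibility check.
- **Inflated bounds.** They count every stopper, including short stays, withdrawn consent and loss to follow-up. The part due to the Section 8 rule is smaller and cannot be separated.

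One objection does not stand: that all this belongs to the analysis plan. What is collected after a participant stops is settled by the protocol, and Section 8 states a rule on it.

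**Conclusion.** The concern holds in a limited form. Followed as written, Section 8 takes participants out of the study for reasons that bear on feasibility or clinical course, and the protocol does not provide for their 30-day exacerbation, readmission or mortality afterwards. Those outcomes can be lost.

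The size is unknown, since every discontinuation rate used above is an assumption. A reader might conclude that the readmission rate will be biased. The documents do not show that: equal loss gives none, and the assumed unequal losses move the rate by less than the sampling error of 30 patients. The primary endpoint is little affected, because once NRD measurement stops, a later exacerbation has no NRD value from the day before to contribute. The case for changing the text is that the loss is avoidable and cheap to prevent.

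**What to change.** Leave the exclusion criteria and the decision to stop measurements unchanged. Limiting the exclusion list to enrolment or discharge would override the criterion on airway pressure after discharge and the skin safeguard, and the problem does not require it.

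- **Sections 8 and 12.2:** state that a participant who meets a criterion after discharge stops study measurements but, consent permitting, stays in the cohort. Data to that day are kept and the reason is reported as a feasibility result. Stays of 24 hours or less remain a deferred eligibility check.
- **Section 9.4:** extend the medical record review to obtain 30-day exacerbation, readmission and mortality for these participants.
- **Section 14.1:** align completion with 9.6 (30 days or readmission) and say how deaths count. Recruiting to 30 completers can stay.

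The cost is a few sentences, a little more review of records the team already consults, and some incomplete NRD series in the cohort.

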## 8.1 Subject inclusion criteria

### Inclusion criteria

- Age 40-80 years
- Patients hospitalized with a primary diagnosis of an acute exacerbation of COPD
- Body mass index (BMI)  $\leq 35 \text{ kg/m}^2$
- Cognitively and linguistically able to follow instructions given in English and provide informed consent
- To be discharged to home following the hospitalization
- Patient lives in the catchment area served by the Lane Fox Unit at Guy's and St Thomas' NHS Foundation Trust in a home environment deemed safe by the investigators to perform home assessments

## 8.2 Subject exclusion criteria

### Exclusion criteria

- Previous home PAP (CPAP or NIV) therapy use within the past year, or post-discharge
- Allergies to latex, metals or local anaesthetic agents
- Wound or inflamed skin at parasternal location (2nd intercostal space)
- History of skin allergies or sensitivity to cosmetics and lotions
- Psychological and social factors that would impair compliance with study protocol and schedule
- Any major non-COPD chronic disease or condition, such as severe heart failure (LVEF<30%), malignancy (active treatment or palliation), end stage renal failure/dialysis, significant neuromuscular disease (e.g. Motor Neuron Disease, Muscular Dystrophy) determined by review of medical history and / or patient reported medical history that may contribute significantly to risk of readmission, as determined by PI
- Length of stay  $\leq 24$  hours
- Planned travel away from home within the 30 day post discharge period

## 9 Study procedures

### 9.1 Subject recruitment

Eligible participants will be identified by the clinical team. The investigator will subsequently approach these patients to discuss recruitment to the study and will be responsible for obtaining informed consent. Recruitment will be achieved through discussion of the project and providing the patient with a comprehensive information leaflet. The patient will be given the opportunity to ask questions concerning the project and their care.

Participants will be provided with at least one hour to decide upon their participation in the study. A longer period can be provided however patients must be recruited within 16 hours of presentation to the Accident and Emergency department of St Thomas' Hospital. Participants will sign a consent form to confirm enrolment into the study.

Participants will not receive payments for study participation.

### 9.2 Screening Procedures

Screening for eligible patients will be undertaken by the clinical team.

### 9.3 Schedule of assessments for each visit

#### Baseline assessments

Enrolled patients will have clinical review and the following data collected at the 1st study assessment:

- The following data will be obtained from electronic patient records:
  - Age, height, weight,
  - Pack year history
  - Comorbidities
  - Medications (acute & chronic)
  - Premorbid data (exacerbation frequency, spirometry (FEV1, FVC, IC), extended Medical Research Council Dyspnoea (eMRCD) score)
  - Chest radiograph
  - Admission venous blood results: Haemoglobin, white cell count (including differential), platelet count, urea, creatinine, C-reactive protein, venous blood gas
  - Arterial blood gas on admission
  - Vital observations (heart rate, blood pressure, respiratory rate, oxygen saturations and supplementary O2 flow rate) at the time of the investigator assessment
- The following data will be obtained by measurements taken by the investigator:
  - eMRCD Score
  - EXACT-PRO questionnaire
  - COPD assessment test (CAT)
  - Body composition (Fat Free Mass)
  - Clinical examination for signs of right and/or left ventricular failure
  - Spirometry – FEV1, FVC, IC
  - Neural respiratory drive (NRD) – resting and maximal manoeuvres to obtain RMS EMGpara (microvolts), RMS as percentage of maximum (EMGpara%max) and Neural Respiratory Drive Index (NRDI). The procedure for NRD measurement is described below.

#### Hospital assessments

Patients will be seen as inpatients by the trial team for clinical review and further physiological characterisation. The following measurements will be performed by the investigator:

- EXACT-PRO questionnaire
- NRD
- Vital observations at the time of the investigator assessment will be obtained from electronic patient records

#### Pre-discharge measurements

The investigator will perform a final study visit on the day of discharge collecting the following data:

- Medications (acute & chronic)
- Up to date venous blood tests (haemoglobin, white cell count including differential, platelet count, urea, creatinine, C-reactive protein) and arterial blood gas if performed by the clinical team. These tests do not need to be performed by the research team.
- Vital observations
- COPD assessment test (CAT)
- EXACT-PRO questionnaire
- Spirometry – FEV1, FVC, IC
- NRD
- Participants will be issued with a wrist-worn physical activity monitor which should be worn for the remaining duration of the study, apart from short periods for personal hygiene

**Home measurements** to be collected by the investigator:

- EXACT-PRO
- Neural respiratory drive (resting and maximal manoeuvres)
- Review of participants' symptom diaries
- COPD assessment test (CAT) (weekly)
- Spirometry – FEV1, FVC, IC (weekly)
- Physical activity monitors will be collected at the final assessment

**NRD measurement**

The NRD measurement device consists of three surface electrodes, shielded cables and a base unit. This is connected to a laptop on which software which analyses raw EMG data to generate a measurement of NRD is installed. The system is used to measure and record 2nd intercostal space parasternal EMG signal, nasal cannula pressure and accelerometer data.

EMGpara will be collected by the investigator using standard medical grade equipment as previously described[3]. In brief, the 2nd intercostal space will be identified by bony landmarks and marked with an indelible marker. Skin preparation will be performed using EMG preparation gel (Nuprep skin prep gel, Weaver and Company, Colorado, USA) followed by detergent wipes (Clinell patient wipe, GAMA healthcare, London, UK) followed by to remove exfoliated skin. Two wet gel electrodes will be placed immediately adjacent to the sternal border in the 2nd intercostal space and one wet-gel electrode will be placed on the clavicle. All electrodes will be connected to the automated EMG analysis system. A nasal cannula will be placed in the nares to detect pressure changes during respiration in order to ensure accurate detection of the inspiratory cycle of respiration. In addition, an accelerometer will be attached to the thorax of the patient.

These 3 modalities (EMGpara, pressure-based respiratory signal and accelerometer) are connected to the automated EMG analysis system. This system is based on the Porti device from the TMSi company. The Porti system is CE certified (class 2A, type CF) and FDA 510k approved. The automated EMG analysis system extends the Porti device by providing bespoke software to capture, visualize and process the received data. The software runs on a laptop computer connected by USB cable to the fibre/USB interface of the Porti. Data is processed by the software to identify the inspiratory portion of the EMG signal and calculate an index of neural respiratory drive, as reported previously (EMGpara in microvolts (µV), EMGpara%max as the ratio to the maximum sniff EMGpara (by instructing the patient to undertake three maximal sniffs) and NRD (product of EMGpara%max and respiratory rate). The processed data (i.e. the indices of NRD) are not displayed online and not provided to the investigator. It therefore cannot influence clinical judgment. The software as tested in the study does not deliver any diagnosis, prevention, monitoring, treatment or alleviation of disease.

Before starting any spot-check NRD measurement, it will be ensured that the participant is seated in a relaxed semi-recumbent position with posture to ensure minimal tonic activity of anterior chest wall muscles. This practically entails participants to be seated with arms supported by arm rests or a pillow on the lap. The process of measuring NRD indices is expected to take approximately 10 minutes. To obtain the measurements of NRD, raw EMGpara, RMS EMGpara and airflow will be obtained over a seven minute 'spot check' period. In the final minute, patients will be asked to perform a minimum of six maximal sniff manoeuvres in order to obtain maximal sniff measurements. This data will be analysed after data acquisition using an automated algorithm to obtain NRD and sniff measurements.

NRD measurements will be recorded by an investigator during participants' hospital stay following the procedure described above. Measurements will be taken twice daily, one pre-SABD and the second

20-minute post-SABD. The timing of NRD measurements should stay consistent throughout their hospital admission.

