#### **9.4 Follow up Procedures**

##### **Hospital Discharge and subsequent readings**

On the day of discharge, vital observations, spirometry (FEV1, FVC, IC) and NRD will be measured and the EXACT-PRO and CAT symptom questionnaires will be completed. The list of discharge medications will be documented. Patients will be issued with physical activity watches on the day of discharge and this should be worn for the remaining duration of the study, apart from short periods for personal hygiene.

The study staff will schedule a time to visit the participant the next day after their discharge. The timing of the visit will be scheduled at the participant's convenience however should remain the same time for the remaining duration of the study. At each visit, the EXACT-PRO questionnaire will be completed and EMG measurements performed. NRD will be analysed after the home visit is completed. A symptom dairy will be recorded along with record of additional medications used which will be reviewed by the investigator. The CAT questionnaire and spirometry (FEV1, FVC, IC) will be performed weekly at home.

If, when during conducting the measurements in the home setting, the assessment of the investigator is that the patient has a significant exacerbation and requires emergency treatment they will use the following traffic light system to provide assistance:

- Green: The participant is clinically stable with an increase in their COPD symptoms – the investigator will signpost the participant to take the course of action they usually would (for example using their rescue pack and/or arranging an appointment with their General Practitioner).
- Amber: The participant is more unwell than category Green but less unwell than category Red – the investigator will signpost the participant to take the course of action they usually would and additionally provide an escalation plan to seek urgent medical attention should they deteriorate (GP appointment or attendance at their local Accident and Emergency department).
- Red: The participant is critically unwell – Investigator will urgently call 999 to request an ambulance.

If the patient requests a medical review the investigator will direct the patient to the usual health care provider for the patient.

The final study visit at day 30 will ensure completion of questionnaires, collection of physical activity monitors and confirmation of health status.

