##### **Medical record review**

The study investigator will corroborate patient reported events with primary care physicians and local hospital electronic patient records to confirm nature and timings of visits.

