### *Hospital discharge and subsequent readings*

Participants will receive home visits by an investigator who will perform NRD measurement, help the participant to complete the EXACT-PRO questionnaire and review participants' symptom diary. The CAT questionnaire and spirometry (FEV1, FVC, IC) will be measured weekly.

The final study visit at day 30 will ensure completion of questionnaires and collection of physical activity monitors.

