### **14.2 Statistical analysis**

For all analyses,  $p<0.05$  will be deemed statistically significant. Comparison of data with one or more factors will be analysed using independent or paired t-test and ANOVA with repeated measures (if needed) for normally distributed data, and non-parametric tests in cases of non-normally distributed data, whenever applicable. Measures of association between the defined indices of NRD, the monitored endpoints and routinely used metrics will be investigated (e.g. using regression analysis). At last, univariate and multi-variate logistic regression may be employed to evaluate the predictive value of a number of investigated features (using the Receiver Operating Characteristic Methodology).

Interim analysis will be performed after 5 patients have been readmitted.

[name] (King's College London) will be involved in statistical analysis for the study. The Lane Fox Research Unit has an existing contract with [name] for *ad hoc* statistical support.

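### Withholding the NRD indices does not by itself keep NRD and the exacerbation outcome independent: signals may be visible, one role serves both sides, and event dates need not be settled before NRD is opened

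*Protocol*

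**What the plan says.** **Masking.** Section 9.3 (NRD measurement) states "The processed data (i.e. the indices of NRD) are not displayed online and not provided to the investigator", and draws the conclusion "It therefore cannot influence clinical judgment". The same section describes the system as "providing bespoke software to capture, visualize and process the received data", running on a laptop connected to the recording device.

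**Who does what.** Section 9.3 also says "EMG para will be collected by the investigator using standard medical grade equipment". At home visits, Section 13.1 has the investigator perform the NRD measurement, "help the participant to complete the EXACT-PRO questionnaire" and review the symptom diary. Section 9.4 (Medical record review) adds: "The study investigator will corroborate patient reported events with primary care physicians and local hospital electronic patient records to confirm nature and timings of visits".

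**When NRD is analysed.** Section 9.4 says "NRD will be analysed after the home visit is completed". It names no analyst and no latest time, and does not link the analysis to confirmation of events. Section 14.2 adds "Interim analysis will be performed after 5 patients have been readmitted".

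**What depends on the outcome.** The primary endpoint (7.1) is the change in NRD from baseline to the day before an exacerbation. The primary objective (Section 6) specifies a symptom-based definition of re-exacerbation. Section 5 ranks three event types: COPD-related admission, physician-assessed exacerbation, and self-treated exacerbation. EXACT-PRO is the comparator in two secondary correlation endpoints and defines recovery in a third endpoint.

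**The concern.** The study asks whether NRD tracks or precedes an exacerbation. That needs two measurements made without knowledge of each other: NRD as the index, and symptoms, event class and onset date as the reference. Masking the computed number is a good first step, but it closes only one route between them.

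Two routes stay open. At the visit, the operator may see the EMG and breathing traces and then help with the questionnaire. After the visit, the indices may exist before the event date is final. An impression that the signal is high could raise an assisted EXACT-PRO score or move an uncertain onset date. Either would tend to strengthen the NRD–symptom correlations or enlarge the primary change, and so favour NRD. For a pilot whose data are meant to size a validation study, that error would carry forward.

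**Working it through.** The protocol gives no figure on this point, so the check compares its sections. One calculation concerns the timing of the interim analysis.

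**1. Does the premise support the conclusion?** The premise is that indices are neither shown in real time nor handed to the investigator. The conclusion is that they cannot affect judgment. Two gaps lie between them.
- The indices are built from EMG amplitude, maximal sniff EMG and, for the NRD index, respiratory rate. The system acquires and can visualise these signals. No section restricts what the operator sees.
- Real-time display is excluded, but the analyst is not named and access to the output after the visit is governed only by the general statement.

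**2. Are the two sides kept apart by role or by order?** Not by role: one role records the EMG, helps with EXACT-PRO, reviews the diary and corroborates events. Not by order: no section says whether the questionnaire and diary come before or after the EMG.

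**3. Is the reference fixed before the index is opened?** Section 9.4 sets only an earliest time for NRD analysis. No section requires class and onset date to be settled first.

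**4. How much room is there in the onset date?** It varies with the event type in Section 5.
- Admission: dated by hospital records.
- Physician-assessed: the contact is dated by primary care or hospital records.
- Self-treated: no physician assessment by definition, so possibly no outside record.

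Record review confirms the nature and timing of visits. The endpoint needs the date of exacerbation onset, which can precede a visit.

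**5. Would the interim analysis fall while events are still open?** Inputs: 30 patients (14.1); 5 readmissions as trigger (14.2); 20% readmitted within 28, taken as days because the unit is missing (Section 11); 2 recruits per week (Section 8). It is assumed that the 20% applies to this cohort and that patients are independent.
- Expected readmissions: 30 × 0.20 = 6.
- Expected position of the fifth: 5 / 0.20 = patient 25.
- Patients in home follow-up at one time: 2 × 30/7 ≈ 8.6.

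| Assumed rate | P(at least 5 in 30) | P(fifth within first 29) |
|---|---|---|
| 15% | 0.48 | 0.44 |
| 20% | 0.74 | 0.72 |
| 25% | 0.90 | 0.88 |

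At the protocol's own rate, the trigger would probably be met with follow-up and event confirmation still running. At 15% it is slightly less likely than not.

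**The case against.** **The masking is real.** The conclusion in 9.3 refers to the processed indices, and no section gives these to the investigator. A reader might infer that the masking claim is false. The documents do not support that: doing several tasks does not reveal a withheld number. What stands is that the absolute wording claims more than the procedures secure.

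**A raw trace is not an index.** Normalised NRD needs inspiratory gating, RMS processing and scaling to maximal sniff, all done later by an algorithm. Visualisation is listed as a software function, without saying what appears on screen at a visit. Respiratory rate can be seen without any device. This stands in part: the traces may give only an impression of the signal, but access to them is not restricted.

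**The traffic light does not classify the endpoint.** A reader might infer that the investigator grades the exacerbation for analysis. Section 9.4 presents the colours as triage for giving assistance, and Section 5 rests on admission, physician assessment or self-treatment. The link is indirect only: Green points the participant to their usual action, which may be a rescue pack or a GP appointment, and so may precede an event in one of those classes.

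**Outside records limit discretion.** True for admissions and physician contacts; less so for self-treated events and for symptom onset.

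**Analysis before events are final is permitted, not stated.** Likewise, 14.2 gives only the interim trigger, not the content or recipients, and a statistical analysis plan may cover them. Both points stand. Visit order, however, is a matter of conduct that a later analysis plan cannot restore.

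**EXACT-PRO completion is not contradictory.** Section 13.1 has the participant complete it at baseline and in hospital, and the investigator help at home. Both can be true.

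**A tempting number.** Suppose the assessor always dated onset to follow the higher of 2 or 3 independent normal readings. With no true change, the mean would be inflated by 0.56 or 0.85 within-patient SD, and a paired t-test on 6 events would reject in about 14% or 27% of trials instead of 5%. If the signal guided dating in half of events, this falls to about 7% or 10%; in a fifth of events, to 5–6%. The worst case needs full knowledge of NRD, which 9.3 withholds, and free dating of every event, which 9.4 limits. The documents do not say where in this range the study would lie.

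**Conclusion.** The concern holds as a gap in protection. The masking in 9.3 is sound as far as it goes, but it does not secure the absolute conclusion drawn from it. Signals may be visible to the operator, the same role contributes to the symptom score and to event confirmation, and class and onset date need not be settled before NRD is opened. The exposure is greatest where the primary endpoint rests on the onset date of a self-treated event.

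The likely direction is in favour of NRD, but the size cannot be derived from the documents. The false-positive rates above illustrate an assumed behaviour and are not an estimate for this study. The likely overlap of the interim analysis with open follow-up (0.72 at the stated rate; 0.44 to 0.88 over assumed rates of 15% to 25%) shows when NRD could be opened early. It does not show that results would reach visiting staff.

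This should be changed because the protection is cheap, not because bias has been shown.

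**What to change.** 1. **Visit order (9.4, 13.1).** At each visit, complete EXACT-PRO, with neutral help if needed, and the diary review before the EMG measurement. Leave clinical triage and safety actions as they are.
2. **Lock before opening NRD (9.4).** After record review, sign off and lock each participant's exacerbation class and onset date before that participant's NRD indices are computed or opened.
3. **Interim access (14.2).** Keep any interim NRD results from staff who visit participants or confirm events.
4. **Wording (9.3).** Replace the absolute conclusion with a statement that the indices are masked but the acquired signals may be visible to the operator.

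**Cost.** A few sentences in the protocol and one sign-off line in the CRF, with no extra assessor. NRD processing for a participant waits until record review is complete.

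**What remains.** The visit order protects a day's score from that day's trace, not from memory of earlier visits. The lock covers the indices, not an impression of the raw signal. These residual risks are worth stating when the results are reported.
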